## **8. Results**

At the beginning of the study, participants who participated in this study amounted to 62 children for control group and 62 children in experimental group. There was no number of excluded participants. The schools was not under any plans of getting other interventions of dental health program during one month intervention period of this study. After random assignment of the groups, all of the participants received the intervention. Lost to follow-up were found with the number of 2 in control group and 4 in intervention group. The participants did not come in the day of follow-up data collection with the reason of sick and family occasion. Using the intention-to-treat method, the number of data analyzed were following the original number allocated, that were 62 for each group. The missing value in follow-up were replaced using the last value obtained, in this case the baseline value was used.

The age of the participants and the percentage of male and female participants between control and intervention group were not significantly different ( $P < 0.05$ ). The

tooth brushing habit of the participants seen from the frequency and the duration of brushing were not significantly different ( $P < 0.05$ ). Snacking and eating frequency that reflected the eating habit of the participants were also not different ( $P < 0.05$ ).

In this study, all of the participants (100%) in the control group can follow the protocol to brush their teeth using natural method. In intervention group, 79% of the participants followed the protocol to brush their teeth using Modified Brush tooth brushing method systematically.

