## 6. Research Procedures

### Participants and setting

One hundred and twenty four students from two state elementary school in Yogyakarta, Indonesia participated in this study. The age of the participants were between 10 and 12 years old including males and females students. All of the participants were fifth graders from Caturtunggal IV State Elementary School and Babarsari State Elementary School. To be eligible to participate in this study, each participants met the criteria including: students with age 10 to 12 years old and willing as well as permitted by the parents/guardian to join thorough the study. The exclusion criterias were not being discovered from them, that were being diagnosed having developmental disorder, using orthodontic appliances, and using antiseptic mouthwash for daily use.

Caturtunggal IV State Elementary School and Babarsari State Elementary School are the government's schools that are placed in the same cluster in one sub-district. These two schools have the similar characteristics in social-economy, number of students, and

the type of school based on the data and recommendation from Education and Culture Office of Sleman District, Yogyakarta, Indonesia. The examinations were done in the terrace in front of the classes to get the sufficient lighting. The training session was done in the class and the schoolyard. Examination and training each lasted approximately 15 minutes and 60 minutes. The examinations were done two times; before and after training with a distance of one month. While the training session were given one time each group after baseline examination. The reinforcement sessions were given to the intervention group once a week in a month after the training session. The reinforcement sessions lasted approximately 20 minutes for each session.

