#### Dependent Variables and Data Collection

The dependent variables in this study were Plaque Index (PI) and Gingival Index (GI). The hypotheses of this study were the plaque level and gingivitis level in subjects using the Modified Circular method is different from that in subjects using natural tooth brushing method and the level of plaque after using the Modified Circular method is different from that before using the method.

*Plaque Index Examination.* Participants' plaque level was measured using Turesky Modification of Quigley Hein (83). Data were collected during baseline and follow-up to track the changing of the plaque level before and after intervention. The tools used in this examination were micro-brush, mouth mirror and probe under the natural light. The procedure was painting all of the exposed tooth surfaces with disclosing solution and the participants were asked to rinse one time. Facial and lingual surfaces of the teeth were examined except third molars. A score between 0 and 5 was given based on the criteria. The plaque scores were recorded on the plaque index examination sheet containing the diagram of the teeth with the separated boxes of facial and lingual/palatal areas. The index was determined by calculating the total score divided by the numbers of the surfaces examined.

Table 1 Scoring criteria of Turesky Modification of Quigley-Hein Index (83)

Score	Criteria
0	No plaque.
1	Separate flecks of plaque at the cervical margin of the tooth.
2	A thin continuous band of plaque (up to one mm) at the cervical margin of the tooth.
3	A band of plaque wider than one mm but covering less than one-third of the crown of the tooth.
4	Plaque covering at least one third but less than two thirds of the crown of the tooth.
5	Plaque covering two-thirds or more of the crown of the tooth.

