*Gingival Index Examination.* The examination of gingival condition was using the Gingival Index (88). Data were collected during baseline and follow-up to track the changing of the gingival condition before and after intervention. The tools used in this examination were mouth mirror under the natural light. The procedure was examining all of the gingiva on the buccal, lingual/palatal, mesial, and distal areas of the teeth. A score between 0 and 3 was given based on the criteria. The Gingival Index were recorded on the gingival index examination sheet containing the diagram of the teeth with the separated boxes of buccal, lingual/palatal, mesial, and distal areas. The index was determined by calculating the total score divided by the numbers of the areas examined.

Table 2 Scoring criteria of Gingival Index (88)

Score	Criteria
0	Normal gingiva.
1	Mild inflammation - slight change in color, slight edema. No bleeding on probing.
2	Moderate inflammation - redness, edema and glazing. Bleeding on probing.
3	Severe inflammation - marked redness and edema. Ulceration. Tendency to spontaneous bleeding.

*Questionnaire.* Personal information; oral health knowledge, attitudes, practices; and eating habits of the participants were recorded using questionnaire. The questionnaire were questioned by interview. Data were collected during baseline and follow-up to check the changing of tooth brushing practice and eating habit that may influence the plaque and gingival index. The back-translation technique had been used to ensure the quality between the English and Indonesian language versions. The interviewer marked

X on the box of questionnaire choice of answers in accordance with the answers of participants.

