#### Data collection procedure

- 1) The researchers well informed the teachers, parents or guardians, and the children about the purpose of the study, the procedure, and the right to continue or withdrawn without any penalties. The parents or guardians of the children who meet the inclusion criteria were asked by the researcher and teachers the permission to their children to participate in this study. Their consent were shown by signing of the consent form.
- 2) The appointment were made with the teachers to set the time to perform examination and intervention to the children.
- 3) Baseline data collection were done to all of the student participating of the study. The children were interviewed by interviewee using structured-questionnaire inside of the class. The oral examinations were done after completing the interview. The oral examination began with the examination of gingival condition and then continued with plaque level examination. Examination area was set outside of the class to get enough light. The children were examined on a chair in sitting position using natural sun light. The examiner was blind to the allocation of the group, the examiner will not know whether the group examined was intervention group or control group. After the oral examination was done, the video recording was taken to the children to record the way the children brush their teeth. The area recorded was only around their mouth and not showing their face.
- 4) In the other day, children in each group were given 2 hours for tooth brushing training course in small groups containing 4-5 children per group. The instructor motivated the children about how to improve oral hygiene for both groups. The

children were instructed to brush their teeth two times per day in two minutes. The control group were instructed to brush the teeth as how they brushed every day. The intervention group were demonstrated about how to brush the teeth using Modified Circular method. After the training in the class was completed, the activity then continued with practiced brushing together in schoolyard. Intervention group were observed once a week to make sure that they did Modified Circular method well without any repetition or addition of intervention. The researcher provided toothbrush and toothpaste to be used by the children during the one-month intervention period.

- 5) Follow up examination were done one month after the training by collecting the same data as baseline.

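### Baseline scores stand in for the missing follow-up of six children under an intention-to-treat label, which forces zero change, and no observed-case result is shown

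*Combined protocol and SAP*

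**What the plan says.** Section 8 (Results) gives the losses: "Lost to follow-up were found with the number of 2 in control group and 4 in intervention group". It gives the reasons without splitting them by group: "The participants did not come in the day of follow-up data collection with the reason of sick and family occasion". It then defines the analysis set, "Using the intention-to-treat method, the number of data analyzed were following the original number allocated, that were 62 for each group", and the rule for the gaps, "The missing value in follow-up were replaced using the last value obtained, in this case the baseline value was used".

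The schedule in section 6 has one baseline and one later examination. Under Participants and setting: "The examinations were done two times; before and after training with a distance of one month". Under Data collection procedure: "Follow up examination were done one month after the training by collecting the same data as baseline". The stated purpose of having both is to measure change, for plaque ("Data were collected during baseline and follow-up to track the changing of the plaque level before and after intervention") and for the gingiva ("Data were collected during baseline and follow-up to track the changing of the gingival condition before and after intervention").

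Section 7 (Statistical analysis) names t-tests, chi-square tests and a 0.05 level. It has no rule for missing data. The plaque and gingival results in section 8 are given as significance statements, with no overall means, mean changes, SDs or confidence intervals, and with no result restricted to the children examined twice.

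**The concern.** With one follow-up visit, the last value obtained is always the pre-training value. The rule therefore asserts that none of the six children changed at all, in a study whose two examinations exist to track change. Sickness or a family occasion on the day does not support that assertion, although it also gives no sign that absence was related to outcome. The design gives no reason to expect exactly zero change in either group: both were motivated, told how often and how long to brush, and given a brush and paste.

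The filled scores then enter the t-test as if measured. Intention-to-treat settles which group a child is analysed in. It does not call for a baseline score to be used as a follow-up score. At stake are the size of the between-group difference, its standard error, and the before/after change in the intervention group named in the specific objectives of section 5.

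**Working it through.** **Inputs from the documents (section 8).** 62 children per group, with 2 control and 4 intervention children absent.

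- Analysed as reported: 62 + 62 = 124, which agrees with the 124 students in section 6.
- Observed: 60 control + 58 intervention = 118.
- Loss: 2/62 = 3.2%, 4/62 = 6.5%, 6/124 = 4.8%. Fisher's exact test of the 4 v 2 split gives p = 0.68.

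**Exact error.** Let a and b be the mean true changes of the absent intervention and control children (negative = improvement). Relative to complete data, replacing them by zero changes the intervention-minus-control difference by

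error = -(4/62)a + (2/62)b.

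Its sign is that of b - 2a. The fill works against the intervention when b > 2a and favours it when b < 2a.

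**Size under assumed caps.** The documents give no mean changes, so the caps of 0.5 and 1.0 points are assumptions.

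| Cap on a and b in absolute value | Same direction, (4/62) × cap | Opposite direction, (6/62) × cap |
|---|---|---|
| 0.5 | 0.032 | 0.048 |
| 1.0 | 0.065 | 0.097 |

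With no cap at all, the six children can move the difference over a span of 5 × 6/62 = 0.48 points on the 0–5 plaque index and 3 × 6/62 = 0.29 points on the 0–3 gingival index.

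**Illustrations if absent children changed like their arm.** Filled difference = (58/62)dI - (60/62)dC, where dI and dC are the arm mean changes. All changes are assumed.

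| dI v dC | True difference | Filled difference |
|---|---|---|
| -1.0 v -0.3 | -0.700 | -0.645 |
| -1.0 v -0.5 | -0.500 | -0.452 |
| -0.5 v -0.5 | 0 | +0.016 |
| -0.25 v -0.5 | +0.250 | +0.250 |
| +0.4 v +0.5 | -0.100 | -0.110 |

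Under the same assumption the intervention group's before/after change shrinks by 4/62 = 6.5%.

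**Standard error.** Assume a common SD of 0.5 to 1.0, changes from 0 to -1.0 in each arm, and independent children, as the plan's t-test does. Write pI = 4/62 and pC = 2/62.

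- Observed-case SE: SD × √(1/58 + 1/60).
- Filled SE, follow-up scores: √{[SD² + pI(1-pI)dI²]/62 + [SD² + pC(1-pC)dC²]/62}. The ratio of filled to observed SE runs from 0.975 to 1.061.
- Filled SE, change scores: the same with SD² replaced by (1-p)SD² in each arm. The ratio runs from 0.951 to 1.039.
- The low ends, an SE understated by about 2.5% and 5%, occur when neither arm changes. For the intervention group's own change, the ratio in that case is 58/62 = 0.935.

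**Effect on the test.** For -1.0 v -0.5 on follow-up scores:

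- SD 1.0: filled t = -0.452/0.183 = -2.47; observed t = -0.500/0.184 = -2.72.
- SD 0.5: filled t = -4.72; observed t = -5.43.

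Both analyses stay significant at 0.05 in these examples.

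A simulation of 20,000 runs (SD 1, baseline/follow-up correlation 0.5, both assumed) agrees. With no true difference, both analyses rejected about 5% of the time. With a true difference of 0.5 SD, observed cases rejected about 77% of the time, and the filled analysis 64% to 73% depending on the control change.

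**The case against.** The strongest reply is that the fill is small and probably conservative. Section 8 reports no overall baseline difference in plaque and lower intervention scores at follow-up. If the intervention arm did change more favourably and absent children resemble their arm, the fill can favour the intervention only when both arms worsened, which is unlikely given what both groups received. Outside that case it pulls toward no difference and cannot explain the reported significance. This stands as far as it goes. It rests on the absent children being like their arm and on mean changes that the documents do not report, so the direction is likely but not shown. A conservative bias would also still misstate the size of the effect.

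Second, dropping the six children makes an assumption too. If they truly did not change, the filled figure is the right one. That is correct, and it is why the observed-case assumption must be stated and the filled result kept beside it.

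Third, moving to a baseline-adjusted model once results are known changes more than the handling of missing data. Running the section 7 t-test on the same 118 children separates the two effects.

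Fourth, the losses, the reasons and the rule are all disclosed. They are, and that deserves credit, but disclosure does not let a reader check the effect when no observed-case means or SDs are given. The standard errors above also treat children as independent although one school was allocated to each arm. That is a separate matter, which neither analysis resolves.

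**Conclusion.** The concern holds. Six of 124 follow-up scores on each index are set to zero change by construction, the intention-to-treat label does not justify this, and no result without the fill is shown. The error formula is exact. The sizes in points, the standard-error ratios and the t values depend on assumed changes and SDs.

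On those assumptions the error is a few hundredths of a point, up to 0.065 if absent children in both arms changed in the same direction by no more than 1.0, and 0.097 if in opposite directions. Its direction cannot be fixed from the documents. The before/after objectives would be affected as well, but section 8 reports no before/after result, so no reported figure is shown to be wrong there. Nothing indicates that the reported significant differences would be reversed. This is a method that should be replaced, not one that by itself overturns the findings.

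**What to change.** - **Main analysis.** For both the plaque and the gingival index, use a baseline-adjusted ANCOVA of the 118 observed children (60 control, 58 intervention) in their allocated group. State the assumption that absence depends only on baseline score and group.
- **Same children, planned test.** Report the section 7 t-test on these 118, so that the effect of removing the fill is not mixed with the change of model.
- **Sensitivity analysis.** Keep the 124-child baseline-carried-forward result, labelled as such.
- **Text.** State the missing-data rule in section 7, and in section 8 separate the intention-to-treat grouping from the fill.

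At minimum, show the 118-child results next to the 124-child results for both indices.

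The cost is one SPSS re-run on data already held and a few sentences in sections 7 and 8. The analysed number falls from 124 to 118. Before any gain from baseline adjustment, the standard error may rise or fall by a few percent. None of this addresses the allocation of one school per arm.

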### ***Plaque index***

Mean of plaque index for all surfaces in baseline were not different ( $P > 0.05$ ). Analyzed from each surface of each sextant, right and left upper lingual posterior surfaces had statistically different mean plaque index ( $P < 0.05$ ) with the higher number of dental plaque in intervention group. However, the anterior upper labial surface of control group had approximately 0.4 points higher number of plaque index than the control group ( $P < 0.05$ ). In follow up mean of plaque index for all surfaces were significantly different ( $P < 0.05$ ) between groups. All of the mean plaque index in intervention group analyzed from every sextant had lower score than the control group and almost all of them were statistically significant ( $P < 0.05$ ).

### ***Gingival Index***

In baseline, there was no differences in mean of plaque index between groups ( $P > 0.05$ ). The intervention group had significant lower mean of gingival index than the control group ( $P < 0.05$ ).

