#### 4. Conceptual Framework

## 5. Objectives

### General objectives

- a. To compare level of plaque of children aged 10-12 years old that use the Modified Circular method and natural tooth brushing method.
- b. To compare level of gingivitis of children aged 10-12 years old that use the Modified Circular method and natural tooth brushing method.

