## **7. Statistical analysis**

All of the data were analyzed using IBM SPSS Statistics 21. The data gathered from the control and the groups were compared using t-test for the mean and standard deviation. A chi-square statistic were used to investigate whether distributions of categorical variables differ from one another. The significance level used in this study was 0.05 for all of the statistical test.

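### As reported, the Gingival Index result cannot support the gingivitis objective: its baseline sentence names plaque, and the gingival difference has no visit and no baseline adjustment

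*Combined protocol and SAP*

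**What the plan says.** General objective b in section 5 is "To compare level of gingivitis of children aged 10-12 years old that use the Modified Circular method and natural tooth brushing method". GI is one of the two dependent variables, and both visits were planned for it: "Data were collected during baseline and follow-up to track the changing of the gingival condition before and after intervention".

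Section 8 reports GI in two sentences. The first is "In baseline, there was no differences in mean of plaque index between groups", with P > 0.05. The second is "The intervention group had significant lower mean of gingival index than the control group", with P < 0.05.

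The Plaque index subsection just above has already given the baseline plaque result ("Mean of plaque index for all surfaces in baseline were not different") and names the visit for its outcome result ("In follow up mean of plaque index for all surfaces were significantly different").

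Section 7 compares the groups by t-test and describes no baseline adjustment. On the threshold it says: "The significance level used in this study was 0.05 for all of the statistical test". Under Experimental Design, one school was allocated to each arm by a coin flip.

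**The concern.** Taken literally, the GI subsection contains no baseline GI comparison, and its one GI result is undated. The only time marker in the subsection is the reference to baseline that opens the first sentence. A reader therefore cannot tell from the text whether the GI difference was found at follow-up, nor whether the two schools started level on gingivitis.

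This matters more here than in an individually randomised trial. With one school per arm, any difference in gingival health between the two schools is fully confounded with the brushing method, and the t-test in section 7 does nothing to take it out. Such differences are plausible: the Plaque index subsection reports significant baseline plaque differences at several sites. At stake is the whole evidence for one of the two general objectives.

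**Working it through.** The documents give no GI mean, SD, difference, power or sample size calculation, so there is no stated figure to reproduce. The main check is of the text.

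**Step 1. The two results subsections side by side.**

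| Item | Plaque index | Gingival Index |
|---|---|---|
| Baseline comparison of its own index | Given, P > 0.05 | Absent; plaque is named instead |
| Visit named for the outcome difference | Follow-up | None |
| Overall mean and SD per arm, difference, CI | None | None |

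The first two rows are specific to GI. The third is a gap shared with plaque. No other section supplies a baseline GI comparison, a follow-up GI value or a change in GI. Both GI sentences are complete and carry P values, so the gap is not one of lost text.

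**Step 2. Inputs for an illustration of the unadjusted test.** There are 62 children per arm (section 8) and alpha is 0.05 (section 7). Three things are assumed: the test is two-sided, which is not stated; children are independent; and a baseline GI difference of d standard deviations persists in full to follow-up with no true effect of the method. The documents give no value for d, so a range is shown.

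**Step 3. Standard error and threshold.** In SD units, SE = sqrt(2/62) = 0.18. The critical value is t(0.975; 122) = 1.980, so an observed difference of about 1.980 × 0.1796 = 0.36 SD reaches P < 0.05.

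**Step 4. Chance of P < 0.05 with no true effect.** By the normal approximation this is Φ(d/SE − 1.96); the other tail is negligible.

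- d = 0.2: Φ(1.114 − 1.96) = Φ(−0.85), about 0.20
- d = 0.3: Φ(1.670 − 1.96) = Φ(−0.29), about 0.39
- d = 0.4: Φ(2.227 − 1.96) = Φ(0.27), about 0.61

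**Step 5. Would correcting the word be enough?** The same figures are the power of a baseline test. If the first sentence were corrected to say that baseline GI did not differ at P > 0.05, a true imbalance of 0.3 SD would still be missed with probability 1 − 0.386 = 0.61. A non-significant baseline test therefore does not establish comparability. The means and SDs at both visits are needed.

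**The case against.** The strongest reply is that this is a wording slip. The sentence stands under the GI heading, baseline plaque had just been reported, and the plaque subsection runs from baseline to follow-up. Read in the same order, the GI subsection says that baseline GI did not differ and follow-up GI was lower. Section 8 has other slips of the same kind: it describes baseline characteristics as not significantly different while giving P < 0.05, it compares the control group with itself on one plaque surface, and it misnames the brushing method once. If the second GI sentence were about baseline, the subsection would contain no outcome result at all. I accept that the slip is the likelier explanation. It remains an inference, and only the sponsor's data can confirm it.

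The reply is also right that the 20% to 61% does not measure the effect of a wrong word. It describes an unadjusted t-test under an assumed imbalance, and would be the same if the sentence named the right index.

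Three stronger readings are tempting and are not supported:

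- A reader might infer that GI was already lower in the intervention school at baseline. The text permits this reading but does not state it, and the parallel with plaque points the other way.
- A reader might infer that baseline GI was never compared. The documents show only that no comparison is reported; GI was to be collected at both visits.
- A reader might infer that the GI claim should be withdrawn. Even if baseline GI did differ, the first step would be the follow-up difference adjusted for baseline, and the conclusion would rest on what that shows.

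**Conclusion.** The point holds for the result as reported. The only evidence offered for general objective b names the wrong index at baseline and gives no visit for the GI difference. This is probably a reporting slip with follow-up intended, and it does not show that the analysis was left undone or that the effect is absent.

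Correcting the wording would settle what was compared and when. It would not settle the cause: with one school per arm and an unadjusted t-test, a lower GI in the intervention group could still be a school difference that preceded the training.

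The size of that risk cannot be computed from the documents. The 20% to 61% is conditional on an assumed, fully persisting imbalance of 0.2 to 0.4 SD and on independent children, which whole-school allocation makes doubtful. It is not an estimate of this trial's error rate.

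Specific objective b, GI before versus after Modified Circular, also has no reported result.

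**What to change.** In section 8, under Gingival Index:

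1. Check the data and correct the index in the first sentence; name the visit in both sentences.
2. Report GI mean and SD per arm at baseline and at follow-up. This also starts to fill the gap for specific objective b.
3. In place of the unadjusted GI t-test, report the follow-up difference between groups adjusted for baseline GI (analysis of covariance), with its 95% CI, and base the GI conclusion on it. Section 7 should be amended to match and should say that this analysis was added after the results were known.
4. State that adjustment does not remove the one-school-per-arm limitation. School and method remain confounded, and the interval treats children as independent.

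The cost is two corrected sentences, four means with SDs, and one adjusted comparison. GI was planned for collection at both visits, so no new data collection should be needed.
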